5.1 Description

Inhaled nitrite (Stage I): Inhaled, nebulized placebo or inhaled nebulized sodium nitrite (80 mg 3 times daily) was given at a minimum of 4 hours apart, with the first dose starting at the beginning of the active part of the day (for example, 8:00, 12:00, and 16:00). The Participant dispersed the doses by at least 4 hours and delivers them over their normal active day time. The doses do not need to be given at the same time each day if the Participant's active period varies by day, for example if the Participant arises later on the weekends.

Inhaled, nebulized sodium nitrite or placebo was administered utilizing the Phillips I-neb AAD nebulizer over 10-15 minutes for each dose. The nebulizer device has a Participant logging system that automatically records adherence and compliance with protocol-specified treatments. The device log was reviewed at the time of ET sessions by the research coordinator with study participants to optimize adherence.

Oral Nitrite (Stage II): Because the inhaled form of nitrite is no longer available, the oral formulation of sodium nitrite will be used in Stage II of the study to test the study hypotheses. Sodium nitrite capsules and matching placebo capsules will be compounded by The University of Iowa Pharmaceuticals, in Iowa City, IA, then shipped to the Research pharmacy at the University of Pittsburgh according to specifications in the IND of [name] for ongoing stability testing, and then study drug will be shipped to Mayo Clinic, where they will be stored and dispensed by the Mayo Clinic Research Pharmacy.

Oral sodium nitrite will be administered at a dose of 40 mg capsule, 3 times daily, using the same dosing frequency as in Stage I of the study with inhaled nitrite. The Participant should disperse the doses by at least 4 hours and deliver them over their normal active day time. The doses do not need to be given at the same time each day if the Participant's active period varies by day, for example if the Participant arises later on the weekends.

Permitted dose adjustment: If significant headache occurs, participants will be encouraged to treat headaches with acetaminophen. If participants cannot tolerate the 80 mg dose of inhaled nitrite, because of headaches, despite acetaminophen, they will be able to down-titrate to the 46 mg dose. If a dose is missed, the 4 hour minimum regimen should be resumed as prescribed with the next scheduled dose. An extra dose or increase in dose should not be taken to make up for the missed dose.

For the oral dose, headaches will be treated with acetaminophen as above. If participants cannot tolerate the study medication 40 mg three times daily even with acetaminophen, the dosage can be reduced to 20 mg three times daily. If 20 mg three times daily is not tolerated, the frequency can be reduced to twice daily or once daily, in consultation with study staff. It will be critically

important that the single day dose be administered 30 minutes prior to exercise training visits and patients will be instructed of this.

If a participant has a temporary discontinuation for reasons other than intolerance, (e.g., such as hospitalization, lost device, etc), the investigator can restart at the last tolerated dose.

Drug interactions: Potential excess nitric oxide mediated effects (e.g., hypotension, headache) might be observed with co-administration of organic nitrates or phosphodiesterase-5 inhibitors or soluble guanylyl cyclase activators. Therefore, co-administration of nitrates, any phosphodiesterase-5 inhibitor formulation or soluble guanylyl cyclase activators is strictly contraindicated due to the risk of hypotension. There are no other known drug interactions and study drug absorption is not affected by food or administration of other inhalers (inhaled steroids or bronchodilators).

52 Treatment Regimen

Inhaled nitrite (Stage I): The dose used for this part of the study was 80 mg three times per day.

Oral nitrite (Stage II): In Stage II of the study, participants will receive an oral dose of 40 mg sodium nitrite or matching placebo three times daily. If there is intolerance, patients may (under the supervision of study staff) down-titrate to 20 mg tid dosing, or 20 mg at lower frequency (as noted above).

53 Method for Assigning Subjects to Treatment Groups

Medidata, Rave, and Balance will be used for clinical data management and randomization. These tools are institutionally supported and allow for rapid database development. The implementation of the software within a project includes training on the system's use, robust error checking, security considerations, and full audit trail. Balance, which is integrated into *Rave*, allows for a variety of randomization and minimization algorithms.

54 Preparation and Administration of Study Drug

Drug dispensing will be managed by the research pharmacy who will obtain and store supplies from the contracted drug supply vendors for both the inhaled and oral nitrite/placebo formulations. At baseline, week 4, and week 8 study visits, participants will receive a sufficient supply of inorganic nitrite or placebo to permit three doses a day for 4 weeks (Stage I). At baseline, and week 4 participants will receive a sufficient supply of inorganic nitrite or placebo to permit three doses a day until final visit (Stage II). To account for potential damage or loss of drug, additional study drug doses will be supplied.

Participants will be instructed to take the medication as required by the protocol, and compliance will be discussed weekly with the participants and assessed every other week (at the time of QOL assessment). Adherence with the inhaled nitrite formulation will also be assessed by download of the compliance data from the nebulizer device, with oral nitrite adherence will be assessed by pill

Inorganic Nitrite To Amplify the Benefits and Tolerability of Exercise Training In Heart Failure With Preserved Ejection Fraction

Revised 16 Jan 2019

counts. Participants will be instructed to bring the nebulizer (Stage I only) and unused drug supplies (inhaled or pills) to study visits where drug is dispensed.

55 Subject Compliance Monitoring

Inhaled nitrite (Stage I): The I-neb device has a Participant logging system that automatically records adherence and compliance with protocol-specified treatments. The device log was reviewed every other week by the research coordinator with study participants to optimize adherence in Stage I.

Oral nitrite (Stage II): Administration of the oral capsule form of nitrite is expected to be much easier for participants compared with the inhaled delivery system in Stage I. Adherence will be encouraged through phone calls with participants and monitored by pill counts at weeks 4, 8, and 12.

56 Prior and Concomitant Therapy

Participants should be treated with standard HFpEF strategies (diuretics for congestion, blood pressure control and heart rate control if Participant is in atrial fibrillation) as per recommended guidelines. Participants should be on stable medications and with adequate blood pressure control prior to entry as outlined in the entry criteria. Further adjustment of diuretics or blood pressure medications during the study period is discouraged and should only be performed according to new and clinically compelling worsening of clinical status. As above, therapy with organic nitrates, phosphodiesterase-5 inhibitors or soluble guanylyl cyclase activators is contra- indicated during the study period.

Data for baseline medication usage will be obtained for descriptive purposes at Study Visit 1.

57 Packaging

The inhaled nitrite drug or matching placebo was supplied in one ml squeezable plastic ampules. The ampules are produced in snap-apart groups of 5 vials and are placed in a nitrogen filled pouch. Participants are instructed to open and utilize one pouch at a time. The medication is stable at room temperature.

The oral nitrite drug or matching placebo using in Stage II will be supplied in capsules compounded by The University of Iowa Pharmaceuticals, Iowa City, IA, then shipped to the Research pharmacy at the University of Pittsburgh according to specifications in the IND of [name] then stored and dispensed by the Research pharmacy at the Mayo Clinic.

58 Blinding of Study

Only research pharmacy staff will be aware of randomization scheme and all study personnel and subjects will remain blinded to the identity of study drug. Placebo and nitrite ampules (Stage I) and capsules (Stage II) have an identical appearance assuring maintenance of the blind.

5.9 Receiving, Storage, Dispensing and Return

5.9.1 Receipt of Drug Supplies

Drug dispensing will be managed by the research pharmacy who will obtain and store supplies from the contracted drug supply vendor. At the first study visit, participants will receive a sufficient supply of inorganic nitrite or placebo ampules (Stage I) or capsules (Stage II) to permit three doses a day for 4 weeks. To account for potential damage or loss of study drug, additional study drug doses will be supplied.

Used and unused investigational product can be destroyed at the site according to accepted pharmacy practice, local and national guidelines, using the site's destruction procedure. A copy of the current investigational product (IP) destruction SOP should be maintained in the pharmacy section of the Regulatory Binder and available for review in case of an audit.

Study IP must not be destroyed until IP accountability has been documented and verified. Study IP destruction should be documented within the Participant Specific IP Accountability Log (or equivalent tracking system).

5.9.2 Storage

Trial products (both unused and in-use) should not be exposed to moisture but can be stored at room temperature. For inhaled nitrite, the plastic ampules come in a nitrogen filled foil pouch in snap-apart groups of 5. Participants are instructed to open one pouch at a time and utilize each ampule before opening another pouch. Oral nitrite is stored at room temperature in accordance with the manufacturer's instructions.

5.9.3 Dispensing of Study Drug

Study drug will be provided by research pharmacy throughout the trial. Study drug may be mailed to participants if circumstances prevent them from collecting the drug in person, cause them to miss scheduled visits or any other unforeseen circumstances arise.

For the inhaled nitrite formulation, the device has a Participant logging system that automatically records adherence and compliance with protocol-specified treatments. The device log will be reviewed every other week at ET sessions by the research coordinator with study participants to optimize adherence. For the oral formulation, adherence will be monitored by study staff using pill counts at follow up visits (see schedule of assessments).

Regular study drug reconciliation will be performed to document drug assigned, drug dispensed, drug returns, and drug remaining. This reconciliation will be logged on the drug reconciliation form, and signed and dated by the study team.

5.9.4 Return or Destruction of Study Drug

Participants are instructed to return all used, partly used and unused trial product at the 12 week visit (4, 8 and 12 week visit for Stage I, which has been completed). Returned trial product(s) (used, partly used or unused including empty packaging material) must be stored separately from the non-allocated trial product(s) until drug accountability has been reconciled. The investigators will keep track of all received, used, partly used and unused trial products.

6 Study Procedures

6.1 Screening Visit 1

At Visit 1, patients will provide written informed consent followed by history and physical examination performed by a cardiologist. Medications will be documented. Participants will complete a blood draw in the CRTU where (NT-proBNP levels, blood methemoglobin, blood sulfhemoglobin, fasting blood glucose and insulin levels will be tested. An optional blood collection drawing an additional 20mL's of whole blood will be collected, separated into serum and plasma by the CRTU and stored by BAP. This will be done at both the screening and final visits and stored for additional testing. We are storing the blood for future analysis and will be examining circulating inflammatory biomarkers, adipokines and how they relate to adipose tissue and HFpEF symptom severity. Assays to be run at a later date will include (subject to change): C-reactive protein (C-RP), Interleukin-3 (IL-1 β), Interleukin 6 (IL-6), Leptin, and Adiponectin. Assessment of endothelial function, baseline echocardiography, dual energy X-ray absorptiometry (DEXA) and a QOL assessment consisting of the KCCQ and SF 36 will be performed. Maximal effort cardiopulmonary exercise testing with expired gas analysis will then be performed with simultaneous echocardiography. Borg symptom severity (effort and dyspnea scores) will be recorded during standardized exercise training at a common objective workload, 2 mph on treadmill at 2° grade for 5 minutes.

Following visit 1 assessments, subjects will be instructed on the use of accelerometer (AXM) devices and devices will be dispensed. Participants are to wear AXM at all times starting at Visit 1. Participants will be randomized in a double-blind fashion at the time but will not start active treatment, and study drug will not be dispensed until the first ET visit (below).

In contrast, Mayo health system participants (who undergo ET visits outside of Mayo Rochester) will receive study drug and supplies during the screening visit, as part of the nebulizer education the participant will be instructed on how to use the nebulizer and will self-administer a saline treatment (for Stage I). Mayo health system participants will be instructed to start assigned study drug the day prior to their initial cardiac rehab visit (ET1).

6.2 Exercise Training (ET) Visits

Following the screening visit 1, subjects will enroll in standard cardiopulmonary exercise training (cardiac rehab) in the Mayo Cardiovascular Health Clinic (CVHC). This will involve ~1 hour sessions 3 times weekly wherein subjects participate in a combination of endurance and strength training as per current practice in the Mayo CVHC. As a result of COVID-19, Mayo Clinic

(Rochester and Health System sites) cardiac rehabilitation centers remain closed or are open with significantly reduced capacity. Thus, we feel it prudent to offer our participants (who are all considered high-risk for contracting COVID-19) a home-based cardiac rehabilitation program (HBCR). This program will model the center-based cardiac rehab program implemented by the Mayo Clinic CVHC. Participants who agree to complete the HBCR program will be seen in clinic for their baseline assessments, 6 minute walk, and given a home exercise protocol. A member from the study team will follow up with patient twice weekly to assess program compliance, discuss successes/barriers with the exercise program, provide modifications to the exercise program (if necessary) and offer support and encouragement.

Once weekly, adverse events, safety and tolerability will be assessed., along with promotion of adherence to training regimen (for example on the third ET visit of each week). For Mayo health system participants this assessment will be done during a weekly telephone call. Every other week, study drug compliance information will be downloaded from the I-Neb device (for Stage I), reviewed, and discussed with the participant. For Mayo health system participants the I Neb device will be downloaded and reviewed during the week 4 visit, week 8 visit and final visit (for Stage I). For Stage II, adherence will be assessed by pill counts at these visits and review of diary.

ET Visit 1:

At the first ET visit (ET1), subjects received training on the use of I-neb device to administer study drug (for Stage I only). For Stage II, subjects will take their first dose of oral study drug 30 minutes prior to the initiation of the ET session (at ET1 and all training visits). One to two days after ET Visit 1, a study team member will call the participant at home to ask about compliance and tolerability of study drug.

Prior to start of exercise training at ET1 and each subsequent ET visit, subjects will administer one dose of study drug (if the Visit is in the morning this will be the first dose of the day, if the Visit is in the afternoon, this will be the second dose of the day but must be separated from the first dose by ≥ 4 hours). For inhaled study drug (Stage I), this was administered immediately prior to ET visit. For the oral study drug (Stage II), the capsule is to be taken 30 minutes prior to the start of the ET visit.

At one of the ET sessions every other week, measurement of QOL will be performed using the Kansas City Cardiomyopathy Questionnaire (KCCQ) and Borg symptom severity (effort and dyspnea scores) will be recorded during standardized exercise training at a common objective workload, 2 mph on treadmill at 2° grade for 5 minutes. Mayo health system participants will complete the KCCQ via biweekly phone visits with the study coordinator.

63 ET Visits 12 (week 4) and 24 (week 8)

At one of the ET visits during week 4 and week 8, the following additional assessments will be performed: New medications over the last 4 weeks will be documented. Blood tests (NT- proBNP levels, blood methemoglobin, blood sulfhemoglobin, fasting blood glucose and insulin levels will be drawn in the CRTU. Data from the accelerometer will be downloaded from the device and the device will be exchanged with a fully charged device. Study drug will be administered prior to

start of training, as at all other ET visits. (Participants will receive additional study drug supplies from research pharmacy for Stage I). Mayo health system participants will be required to do the week 4 and week 8 visits at Mayo Clinic Rochester; they cannot be completed during an ET visit at their participating cardiac rehab site.

6.4 Final Visit

The Final Visit of the drug interventional part of the study for Stage I occurred at week 12

This visit will include all of the assessments performed in Screening Visit 1 (see above). Participants will be asked not to take their study medications the day of this visit; they will be asked to administer a treatment directly prior to the final visit CPET under direct investigator observation. For Stage I, inhaled study drug was administered immediately prior to CPET. For Stage II, oral study drug is administered (under direct observation by study staff) 30 minutes prior to CPET. AXM data will be downloaded and devices returned or changed out. Participants will return all other study materials at the final visit and all unused study drug.

At the Final ET Visit (week 12), participants will be offered enrollment in an ancillary study to evaluate the effects of behavioral/motivational intervention on chronic activity levels and QOL. Subjects agreeing to this part of the trial will then be randomized to behavioral/motivational intervention (motivational phone calls twice weekly with one investigator visit per week) or standard care (no additional contact). Participants will continue to wear AXM devices following this visit to assess how well increases in chronic activity levels are maintained following ET intervention. Involvement in this part of the trial is optional.

Study subjects not participating in the ancillary study will be contacted by phone 2 weeks following the final ET visit (week 12) to verify that there have been no adverse events.

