3.1 General Design

This is a Phase 2 randomized, double-blind, parallel group placebo-controlled trial testing whether inorganic sodium nitrite, as compared to placebo, can enhance the benefits from chronic exercise training (ET) in subjects with HFpEF (see flow diagram below).

Inorganic Nitrite To Amplify the Benefits and Tolerability of Exercise Training In Heart Failure With Preserved Ejection Fraction

Revised 16 Jan 2019

The total duration of the trial is 14 weeks.

Subjects will be screened from the inpatient and outpatient heart failure services and interested qualified subjects will be offered participation. Once consent has been obtained baseline assessment of cardiovascular function and exercise capacity will be performed. All subjects will undergo 12 weeks of ET. Participants will be randomized to receive sodium nitrite 3 times daily or matching placebo 3 times daily during the study period.

In Stage I this was with inhaled medicine for the full 12 weeks of ET. In Stage II, study drug will be administered using an oral preparation for the full 12 weeks. Study subjects will wear accelerometry devices to track daily activity levels at home.

At the Screening visit, during consent, subjects will be given the option to participate in an optional MRI sub-study where they will be asked to complete 2 Magnetic Resonance Imaging (MRI) scans. One scan will be completed prior to or as close as possible to the beginning of cardiac rehabilitation, the other within 2 weeks of completing week 12 of ET (for Stage II). A hematocrit will need to be obtained prior to the MRI if not already drawn within the past 30 days. We will evaluate adipose tissue content and cardiac structure and function. We will determine whether these variables relate to exercise capacity/intolerance in participants, and evaluate how they change with ET with or without nitrite. Subjects will be excluded from this optional substudy if they have contraindications to MRI including aneurysm clips, cardiac pacemakers, internal defibrillators, severe claustrophobia and pregnancy. Women of childbearing potential will undergo a urine pregnancy test; positive test results will yield exclusion from study participation. Patients will be excluded for contraindications to gadolinium-based MRI contrast material, namely glomerular filtration rate less than or equal to 30ml/min.

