6.5 Ancillary Study Visits

6.5.1 Weekly Ancillary Study Visits

Subjects who agree to participate in the ancillary study will be randomized to standard care or behavioral/motivation intervention (once weekly visits with investigator +2 phone calls per week) to evaluate durability of ET effects.

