6.5.2 Final Ancillary Study Visit

The final ancillary study visit will occur 8-10 weeks after ET Visit 36. This visit will include a safety assessment, DEXA, cardiopulmonary exercise test, AXM return and final data download, repeat QOL assessment, Borg symptom severity (effort and dyspnea scores) will be recorded during standardized exercise training at a common objective workload, 2 mph on treadmill at 2° grade for 5 minutes.

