For this study, the study treatment follow-up period is defined as 2 weeks following the last administration of study treatment. The study period during which adverse events must be reported is normally defined as the period from the initiation of any study procedures to the end of the study treatment follow-up.

Preexisting Condition

A preexisting condition is one that is present at the start of the study. A preexisting condition should be recorded as an adverse event if the frequency, intensity, or the character of the condition worsens during the study period.

General Physical Examination Findings

At screening, any clinically significant abnormality should be recorded as a preexisting condition. At the end of the study, any new clinically significant findings/abnormalities that meet the definition of an adverse event must also be recorded and documented as an adverse event.

Post-study Adverse Event

All unresolved adverse events should be followed by the sponsor-investigator until the events are resolved, the subject is lost to follow-up, or the adverse event is otherwise explained. At the last scheduled visit, the sponsor-investigator should instruct each subject to report, to the sponsor-investigator, any subsequent event(s) that the subject, or the subject's personal physician, believes might reasonably be related to participation in this study.

Hospitalization, Prolonged Hospitalization or Surgery

Any adverse event that results in hospitalization or prolonged hospitalization should be documented and reported as a serious adverse event unless specifically instructed otherwise in this protocol. Any condition responsible for surgery should be documented as an adverse event if the condition meets the criteria for an adverse event.

Neither the condition, hospitalization, prolonged hospitalization, nor surgery are reported as an adverse event in the following circumstances:

- Hospitalization or prolonged hospitalization for diagnostic or elective surgical procedures for a preexisting condition. Surgery should **not** be reported as an outcome of an adverse event if the purpose of the surgery was elective or diagnostic and the outcome was uneventful.
- Hospitalization or prolonged hospitalization for therapy of the target disease of the study, unless it is a worsening or increase in frequency of hospital admissions as judged by the clinical investigator.

82 Recording of Adverse Events

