15.1 Schedule of Assessments

	A	B	C	D	E	F	G	H	I	J	K	L	M	N
1							Primary Study:							
2	Visit windows	Screening Visit/ Day -7	Day -14	Baseline Visit/ ET 1/Day 0	Phone f/u Day 1 to 2	Weeks 1 - 3	Wk 4	Weeks 5 - 7	Wk 8	Week 9	Week 10	Final Visit/Week 12	2 Week f/u Visit	Wks 37 to 46 ^c
3	Informed Consent	X												
4	Medical Hx	X												
5	Medication Review	X					X		X			X		
6	Physical Exam	X										X		
7	NYHA class	X										X		
8	CPET	X										X		X
9	Hemodynamic Echo	X										X		
10	Lab evaluation ^a	X					X		X			X		
11	Pregnancy Test	X										X		
12	DEXA Scan	X										X		X
13	Endothelial Function (Endopat)		X									X		
14	QOL assessment (KCCQ)	X	X			Wk 2	X	Wk 6	X		X	X		X
15	IPAQ	X										X		
16	SF-36 Questionnaire	X										X		X
17	Randomization	X												
18	Study Drug Education	X	X											
19	Dispense Study Drug		X					Wk 5						
20	Collect un-used study drug						X		X			1x/wk		
21	Study drug compliance assessment and education			X	1x/wk	1x/wk	1x/wk	1x/wk	1x/wk	1x/wk				
22	Study drug accountability/ pill counts											X		
23	Accelerometer Education	X												
24	Dispense / Exchange / Return accelerometer	X					X		X			Wk 12		X ^b
25	Accelerometer Data download						X		X			Wk 12		X ^b
26	Exercise Training		X		3x/wk	3x/wk	3x/wk	3x/wk	3x/wk	3x/wk				
27	Borg Symptom Severity & Exercise Tolerance	X			1x/wk	1x/wk	1x/wk	1x/wk	1x/wk	1x/wk	X			X
28	AE assessment		X	X	1x/wk	X	1x/wk	X	1x/wk	1x/wk	X	X		X
29	Optional MRI Study	X (1)										X		X
30	Optional whole blood, lab draw study	X										X		X
31		ANT pro BNP, sulfhemoglobin, methemoglobin, fasting blood glucose and insulin levels. (1)Optional MRI will be performed prior to or as close to the start of exercise as scheduling allows.		^a Phone call to take place if not participating in the ancillary study	^b Participants randomized to behavioral/motivational intervention will have once weekly visits with investigator and 2 phone visits per week	^c Exchanged/Dispensed Pleium accelerometer and download data								IRB 16-001467 V11 Nov. 2019

15 Attachments

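### Completers randomised to ancillary standard care have no guaranteed safety contact during the protocol's own 2-week post-treatment adverse-event window

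*Combined protocol and SAP*

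**What the plan says.** Section 8.1 (Adverse Event Reporting Period) states that "the study treatment follow-up period is defined as 2 weeks following the last administration of study treatment", and that adverse events must be reported up to the end of that follow-up. Section 6.4 places the last Stage II dose at the Final Visit, taken under observation 30 minutes before the exercise test.

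For completers, the 2-week contact is described in section 6.4: "Study subjects not participating in the ancillary study will be contacted by phone 2 weeks following the final ET visit (week 12) to verify" the absence of adverse events. The footnote to the Schedule of Assessments (15.1) carries the same condition: "Phone call to take place if not participating in the ancillary study".

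Participants who join the ancillary study are randomised to one of two arms. One is "behavioral/motivation intervention (once weekly visits with investigator +2 phone calls per week" (section 6.5.1). The other is "standard care (no additional contact" (section 6.4). Section 6.5 lists nothing for the second arm before the closing visit: "The final ancillary study visit will occur 8-10 weeks after ET Visit 36" (section 6.5.2). That visit includes a safety assessment.

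Section 4.4.2 has withdrawn subjects contacted 2 weeks after their last dose. Section 8.2 requires specific questioning about adverse events at each contact with a subject.

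**The concern.** The protocol sets a period in which adverse events must be reported, then removes by rule the only call that would close that period for one identifiable group of completers. A patient who finishes all 12 weeks and goes to ancillary standard care is guaranteed less post-treatment safety follow-up than a patient who withdraws.

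Because section 8.2 ties adverse-event questioning to contacts, how completely events are found depends on how many contacts there are. That number differs between the two ancillary arms, and between each arm and the non-participants. At stake is how complete and how prompt the safety data are in the fortnight after treatment stops. For some patients that fortnight also contains a second muscle biopsy or contrast MRI.

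The back-up is weak. Section 8.1 has subjects told to report later events at their last scheduled visit, which for an ancillary participant can be read as the closing ancillary visit.

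**Working it through.** The plan gives no figure of its own to reproduce. The check is a timeline, a count of contacts and a range for the number of patients.

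**Timeline**
- ET Visit 36, at 3 sessions a week (section 6.2): 36 / 3 = week 12.
- Last dose, at the Final Visit (section 6.4): about week 12.
- Window closes (section 8.1): 12 + 2 = week 14.
- Final ancillary visit (section 6.5.2): 12 + 8 = week 20 to 12 + 10 = week 22.
- Gap from close of window to that visit: 20 - 14 = 6 weeks to 22 - 14 = 8 weeks.

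**Scheduled contacts after the Final Visit and up to week 14**

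| Group | Source | Contacts |
|---|---|---|
| Ancillary behavioural arm | 6.5.1 | (1 visit + 2 calls) x 2 weeks = about 6 |
| Completers outside the ancillary study | 6.4 | 1 |
| Withdrawn subjects (2 weeks from their own last dose) | 4.4.2 | 1 |
| Ancillary standard care | 6.4, 6.5 | 0 guaranteed |

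**Incidental contacts that might fill the zero**
- Second MRI: "the other within 2 weeks of completing week 12 of ET (for Stage II" (section 3.1). It would normally bring a contact by the close of the window, but only for volunteers to that substudy.
- Second biopsy: optional, and timed only as close as possible to the end of training (section 6.5.3).
- Accelerometer exchange: at least every 4 weeks (Study Assessments). It could fall inside the window, but nothing requires it to.

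Section 8.2 would require adverse-event questioning at any of these. None is planned for the whole arm.

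**Number of patients**
- The ancillary study is offered at week 12, so the base is completers. Section 7.2 plans 51 Stage II patients with complete data.
- Uptake is not stated; 25-75% is assumed. The allocation ratio is not stated; 1:1 is assumed.
- Low: 51 x 0.25 x 0.5 = 6.4. High: 51 x 0.75 x 0.5 = 19.1. That is about 6-19 patients.

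**Schedule header**
The ancillary column in 15.1 is headed Wks 37 to 46, which does not match weeks 20-22. Since 36 + 1 = 37 and 36 + 10 = 46, the numbers may continue the count from ET Visit 36. The column could then stand for the whole ancillary period or for its final visit. The text does not settle which.

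**The case against.** Several stronger readings are tempting, and the documents do not support them.

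- *No adverse events are ever solicited for this period.* The final ancillary visit includes a safety assessment, so events are asked about, but 8-10 weeks after ET Visit 36 and by recall. Collection is delayed and not necessarily lost.
- *Post-treatment event rates will be too low.* Under-ascertainment is possible, but nothing in the documents shows its size or that it must occur.
- *Events from the final maximal exercise test are missed.* The test takes place at the Final Visit, where section 8.2 requires questioning, so acute events there are outside the gap.
- *Late biopsy or MRI complications go unreported.* Section 8.2 requires serious events after the study period that are at least possibly related to treatment or participation to be reported immediately, and section 8.1 has unresolved events followed. What remains is new, non-serious late events, a separate and smaller question.
- *The schedule header means a wait until weeks 37-46.* Sections 3.1 and 6.5.2 both give 8-10 weeks, and the extracted table is visibly disordered. The header is an inconsistency and does not measure the delay.
- *Trial comparisons are biased.* The ancillary endpoints in section 3.3 do not include adverse events, and no bias in the nitrite-placebo safety comparison is shown.

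It is also fair to say that plasma nitrite returns to baseline by 3 hours after a single oral dose (section 1.1), so late acute drug effects are less likely. That bears on how many events to expect. It does not alter the fact that the protocol chose a 2-week window and leaves one group without a guaranteed contact in it.

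**Conclusion.** The concern holds in a limited form. A stated rule in section 6.4, repeated in the schedule footnote, leaves ancillary standard-care completers with no guaranteed safety contact between about week 12 and about week 14. Their next planned safety assessment comes 6-8 weeks after the reporting window closes, so events in the window may be under-ascertained.

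The number affected, about 6-19, rests on assumed uptake of 25-75%, an assumed 1:1 allocation and the 51 planned Stage II completers. Some of these patients may have an incidental contact through a substudy visit or a device exchange. The primary endpoint is untouched. This is an inexpensive improvement to safety ascertainment that is worth making.

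**What to change.** In section 6.4 and the schedule footnote, remove the condition on ancillary participation so that the 2-week safety call applies to every participant. Time it from the last dose, as sections 8.1 and 4.4.2 do. Use the same short, safety-only script in both ancillary arms.

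The cost is a wording change and one brief call per ancillary participant. The call departs slightly from the no-contact definition of standard care, but it is the same in both arms and so does not unbalance the ancillary comparison.

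Separately, reconcile the Wks 37 to 46 header in 15.1 with section 6.5.2. The sponsor should state what the column is meant to cover before relabelling it.
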